15.8 Pregnancy Test

Pregnancy testing (serum β -HCG) will be performed at screening and 30 days post-treatment. A listing will display all the results as presented in "Pregnancy Test" eCRF page.

16 Analyses of Other Endpoints

16.1 Pharmacokinetics

16.1.1 General Considerations

Population: PK analysis set

Pharmacokinetic parameters will be calculated using actual collection time data where available. There will be no rounding of actual time values, and full precision values will be used as calculated from eCRF data. In the case that the actual time is not available, the scheduled time will be used. Predose samples that occur before drug administration will be assigned a time of 0 hours for that FD, as if the sample had been taken simultaneously with the study drug administration.

Values below the lower limit of quantitation of the assay (LLOQ) will be taken as zero for summary statistics of PK concentration data.

In case of concentrations above the upper limit of quantitation (ULOQ) the numeric value of the actual ULOQ of the bioanalytical assay may be used for preliminary, draft PK evaluations only. For final evaluations >ULOQ values are not accepted and should be replaced by valid numeric values from dilution measurement.

Missing concentrations (e.g., no sample, insufficient sample volume for analysis, no result or result not valid) will be reported and used generally as "N.R.". There will be no imputation for missing concentrations.

Pharmacokinetic concentrations which are erroneous due to a protocol violation, as defined in the clinical trial protocol (CTP), documented handling error or analytical error (as documented in the bioanalytical report) may be excluded from the PK analysis if agreed upon with sponsor PK analyst/clinical pharmacologist prior to performing the statistical analysis. Any PK concentrations excluded from the PK analysis set will be listed and flagged, and the rationale for exclusion will be listed and provided in the CSR. Any other PK concentrations that appear implausible to the Pharmacokineticist must not be excluded from the analysis. Any implausible data will be discussed in the CSR.

Individual PK concentrations in plasma for M3541 will be listed and summarized by dose and fraction day using standard descriptive statistics. A listing of PK blood sample collection times as well as derived sampling time deviations will also be provided.

Pharmacokinetic parameters for M3541 will be listed and summarized by dose and fraction day using standard descriptive statistics (see TFLs for further information). PK parameters derived with inclusion of flagged concentrations will not be used in the descriptive statistics.

Dose proportionality will be presented graphically as follows:

Scatter Plot of individual and geometric mean AUC and C_{max} versus Dose on a linear scale, using AUC_{0-∞}, AUC_(0-t), AUC_{0-∞} and C_{max} derived from FD1 and using AUC_(0-t), and C_{max} derived from FD9.

Individual concentration-time profiles by subject will be created using the actual time points and the numeric concentration data. Arithmetic mean concentration-time profiles by dose and fraction day will be provided using scheduled (nominal) time points and the numeric concentration data. All concentration-time plots for PK data will be presented both on a linear and on a semi-logarithmic scale. Mean plots will include SD error bars when plotted on a linear scale. Additional plot presenting overlay of the arithmetic mean concentrations for each dose level will be provided on a semi-log scale (see TFLs for further information).

The trough concentrations (C_{trough}) will be listed and summarized by dose, using standard descriptive statistics. Individual C_{trough} values will be plotted against actual fraction day on a linear scale, for all subjects by dose. Arithmetic mean $C_{trough} \pm SD$ will also be plotted by dose, on a linear scale.

16.1.2 Estimation of Individual Pharmacokinetic Parameters

Population: PK analysis set

The final analysis will be performed IQVIA and reviewed by the Clinical PK/PD Group of quantitative pharmacology (QP), Merck, Darmstadt, Germany. Standard non-compartmental methods will be used to calculate PK parameters using the actual administered dose and the actual elapsed time since dosing, given with a precision of 14 significant digits or the SAS format Best12. In cases where the actual sampling time or dose is missing, calculations will be performed using the scheduled time or dose level. Otherwise, there will be no further imputation of missing data. The following PK parameters will be calculated for the determination of the PK profile of M3541, where appropriate for Fraction Day 1, 2 to 6, or 9:

Symbol	Definition
AUC _{0-6h}	The area under the concentration-time curve (AUC) from time zero (= dosing time) to the 6-hour sampling time. Calculated using the mixed log linear trapezoidal rule (linear up, log down). (FD 1 and 9 only)
AUC _{0-t}	The AUC from time zero (= dosing time) to the last quantifiable sampling time (t _{last}) at which the concentration is at or above the lower limit of quantification. Calculated using the mixed log linear trapezoidal rule (linear up, log down) (FD 1 and 9 only).

Symbol	Definition
AUC _{0-t} /Dose	The Dose normalized AUC from time zero to the last sampling time (t _{last}) at which the concentration is at or above the lower limit of quantification. Normalized using the actual dose, using the formula AUC _{0-t} /Dose. (FD 1 and 9 only)
AUC _{0-∞}	The AUC from time zero (dosing time) extrapolated to infinity, based on the predicted value for the concentration at t_{last} , as estimated using the linear regression from λ_z determination. AUC _{0-∞} =AUC _{0-t} +C _{last pred} / λ_z . (FD 1 only)
AUC _{0-∞} /Dose	The Dose normalized AUC from time zero extrapolated to infinity. Normalized using actual dose, using the formula $AUC_{0-\infty}/Dose$. Predicted $AUC_{0-\infty}$ should be used. (FD 1 only)
AUC _{0-τ}	The AUC from time zero (dosing time) extrapolated to the end of the dosing interval (24 h). (FD 9 only)
CL/f	The apparent total body clearance of drug following extravascular administration, taking into account the fraction of dose absorbed. $CL/f = Dose/AUC_{0-\infty}$. Predicted $AUC_{0-\infty}$ should be used. (FD 1 only)
CL _{SS/f}	The apparent total body clearance of drug at steady state following extravascular administration, taking into account the fraction of dose absorbed. $CL_{ss//f} = Dose / AUC_{0-\tau}$ where $AUC_{0-\tau} = AUC$ extrapolated to 24h (FD 9 only)
C_{max}	Maximum observed concentration for each fraction day. (FD 1 and 9 only)
C _{max} /Dose	The dose normalized maximum concentration. Normalized using the actual dose, and the formula $C_{\text{max}}/Dose$. (FD 1 and 9 only).
C _{trough}	The concentration observed immediately before next dosing (corresponding to predose or trough concentration for multiple dosing). (FD 2 to 6 and FD 9)
C _{2.25h}	The concentration observed at 2.25 h post dose. (FD 1-6 and 9)
C _{min}	Minimum observed plasma concentration collected during a dosing interval. (FD 9 only)
Cavg	Average plasma concentration during a dosing interval. $C_{avg} = AUC_{0-\tau}/\tau$. (FD 1 and 9 only)

Symbol	Definition
R _{acc(AUC0-6h)}	The accumulation ratio to assess the increase in exposure via AUC_{0-6h} . $R_{acc(AUC0-6h)}=(AUC_{0-6h} \text{ after multiple dose}) / (AUC_{0-6h} \text{ after single dose}). (FD 9 only)$
R _{acc(Cmax)}	The accumulation ratio to assess the increase in maximum concentration with multiple dosing. $R_{acc(Cmax)} = (C_{max} \text{ after multiple dose})/(C_{max} \text{ after single dose})$ (FD 9 only)
t _{1/2}	Apparent terminal half-life. $t_{1/2} = \ln (2)/\lambda_z$. (FD 1 only)
t _{max}	The time to reach the maximum observed concentration collected during a dosing interval (unless otherwise defined, take the first occurrence in case of multiple/identical C _{max} values). (FD 1 and 9 only)
t _{min}	The time to reach the minimum observed concentration collected during a dosing interval. (FD 9 only)
Vz/f	The predicted apparent volume of distribution during the terminal phase following extravascular administration, based on the fraction of dose absorbed. $V_z/f = Dose/(AUC_{0-\infty}*\lambda_z)$ following single dose. (FD 1 only)
λ_z	Terminal first order (elimination) rate constant. Determined from the terminal slope of the log-transformed concentration curve using linear regression on terminal data points of the curve. (FD 1 only)

FD 9 parameters should only be included in descriptive statistics if 4 consecutive days of treatment with no interruption were given to the patient. PK parameters not included in descriptive statistics will be flagged. Any flags should be included in the study specific SDTM/ADaM.

The following PK parameters will be calculated for diagnostic purposes (Fraction Day 1 only) and listed, but will not be summarized:

- The time interval (h) of the log-linear regression ($\lambda_{z \text{ low}}$, $\lambda_{z \text{ upp}}$) to determine λ_z .
- Number of data points (N_{λ}) included in the log-linear regression analysis to determine λ_z .
- Goodness of fit statistic (Rsq,adj) for calculation of λ_z .

The AUC from time t_{last} extrapolated to infinity given as percentage of $AUC_{0-\infty}$ AUCextra% = (extrapolated area/AUC_{0-∞})*100 The regression analysis should contain data from at least 3 different time points in the terminal phase consistent with the assessment of a straight line on the log-transformed scale. Phoenix WinNonlin best fit methodology will be used as standard. The last quantifiable concentration should always be included in the regression analysis, while the

concentration at t_{max} and any concentrations <LLOQ which occur after the last quantifiable data point should not be used.

AUCextra% should be < 20%, the coefficient of correlation (Rsq, adj) should be \ge 0.8 and the observation period over which the regression line is estimated should be at least two-fold the resulting $t_{1/2}$ itself. If these criteria are not met, then the rate constants and all derived parameters (e.g., CL, and Vz, etc.) will be included in the parameter outputs and descriptive statistics but will be flagged and discussed appropriately. Any flags should be included in the study specific SDTM/ADaM.

Partial areas AUC_{0-6h} should be calculated using the scheduled dosing interval, as defined in the CTP. The actual dosing interval calculated from eCRF time data should not be used. The following rules apply when calculating the partial area AUC_{0-6h} within the observed time interval from T_1 to T_2 :

- If the start time of the interval (T₁) occurs before the first observation, the observation at T₁ will be estimated using the linear interpolant between the first data point and initial concentration at time zero (C0). For single dose data C0= 0 when the drug was administered via an extravascular route or via infusion, and C0 is the estimated dosing time intercept when the drug was administered as an IV bolus. For steady state models, C0 is the minimum concentration value occurring within the time interval T₁ to T₂.
- If either T₁ or T₂ falls within the time range in which samples were taken, but does not
 coincide with an observed data point, then a linear or logarithmic interpolation is
 performed to estimate the corresponding concentration value. Whether a linear or
 logarithmic interpolation is used will depend on the method of AUC calculation, e.g.,
 linear up log down.
- If the end time of the interval (T₂) occurs after the last measurable concentration and the terminal regression (λ_z) is estimable, then λ_z is used to estimate the concentration at time T₂. The log trapezoidal rule will be used to calculate the area from the last observation time to the end time of the partial area (T₂). If λ_z cannot be estimated the partial area will not be calculated.

Potential drug accumulation will be evaluated by individual accumulation ratios for AUC_{0-6h} , C_{max} , $R_{acc(AUC_{0-6h})}$ and $R_{acc(C_{max})}$ (that will be calculated by dividing the values obtained after multiple dose (e.g., on Fraction Day 9) by the values obtained after single dose (e.g., Fraction Day 1) and summarized descriptively for each dose level.

Concentrations below LLOQ, which are before the last quantifiable data point, will be taken as zero for calculating the AUC. Unless otherwise specified in the CTP, predose samples that occur before the first drug administration will be assigned a time of 0 hours, as if the sample had been taken simultaneously with the study drug administration. The same applies to the very first predose sample of a multiple-dose study.

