#### Table 4 Electrocardiogram, Pharmacokinetic, and Biomarker Assessments: M3541 Once per FD Dosing Schedule

ECG = electrocardiogram; FD = Fraction Day (days when RT and M3541 are given); PK = pharmacokinetics; PTD = post-treatment day.

a. 12-lead resting ECGs will be obtained after the subject has been in semi-supine position for at least 5 minutes and evaluated by the Investigator for safety assessment. All ECGs should be collected prior to any blood draws for routine clinical laboratory samples or any associated PK blood sample draws. The ECG should be obtained using a Holter recorder. An ECG on PTD 1 is only required if the PTD 1 optional PK sample is drawn.

b. At the indicated times, additional digital ECG recordings equivalent to triplicate ECGs are to be recorded for quantitative analysis by a central ECG laboratory (after the end of the study). The ECG recordings must be acquired immediately prior to the PK sample scheduled for the same time point. The ECG should be obtained using a Holter recorder.

- c. The 8 and 12 hour PK samples and ECG assessments are optional.
- d. The 72 and 240-hour timepoints correspond to PTD 1 and 8, respectively. The 72-hour PK sample is optional and will only be taken if the patient has a visit on PTD 1.
- e. The predose sample should be taken within 1 hour before dosing at each sampling day. PK and pharmacodynamic sampling should occur after any required ECG recording.

Table 5Electrocardiogram, Pharmacokinetic, and Biomarker Assessments: Thrice Weekly Intermittent M3541Dosing Schedule: Monday / Wednesday / Friday

	Predose	Hours Postdose (± minutes)										
		1 (± 5)	3 (± 30)	4 (± 30)	6 (± 30)	8 (± 30)	12 (± 30)	24 (± 120)	26 (± 120)	72 (± 24h)	240 (± 24h)	
Electrocardiogram a												
FD 1 (M3541 dosing)	Xp	Xp	Xp	Xp	Xp	X b,c	X b,c	X b,d	X b,d			
FD 3, 5, 6, and 8 (M3541 dosing)	Х		Х									
FD 10 (M3541 dosing)	Xp	Xp	Xp	Xp	Xp	X b,c	X b,c			X b,e	X b,e	
Pharmacokinetic f												
FD 1 (M3541 dosing)	Х	Х	Х	Х	Х	Xc	Xc	Xd	Xď			
FD 3, 5, 6, and 8 (M3541 dosing)	Х		Х									
FD 10 (M3541 dosing)	Х	Х	Х	Х	Х	Xc	Xc			Xe	Xe	
Plasma protein determination												
FD 1	Х											
FD 10	Х											
Pharmacodynamic marker CC												
FDs 1, 6, and 8	Х	Х	Х					FD 1 only				
FD 2	Х											
Immune cell sampling f												
FDs 1, 6, and 9	Х											

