15.7 ECG and QT/QTc evaluations

Population: SAF analysis set

Electrocardiogram values based on "Electrocardiogram" eCRF page will be used for summary statistics and shift tables.

Time of ECG collection will be expressed both as actual and nominal (i.e. expected) time elapsed from first M3541 administration in hours, derived as defined at section 9. The following spider graphs will be produced separately using actual and nominal times for QTcF, as collected in the eCRF. Three. Three plots per dose level will be produced, with one curve per subject according to the specifications below:

- 1. Overall: Time point (in hours) on the x-axis (From -1 to 250) vs. QTcF observed value on the y-axis (i.e. results collected 72 and 240 hours post fraction 9 dose will not be presented)
- 2. Fraction Day 1: Time point (in hours) on the x-axis (From -1 to 12) vs. QTcF observed value on the y-axis
- 3. Fraction Day 9: Time point (in hours) on the x-axis (From 240 to 250) vs. QTcF observed value on the y-axis.

ECG parameters on-treatment will be presented by the following frequency table (by dose level and overall):

- Shift from normal baseline result to any abnormal post-baseline result (i.e. maximal ontreatment value)
- Worst absolute QTcF interval post-baseline
 - \circ > 450 ms and \leq 480 ms
 - \circ > 480 ms and <500 ms
 - \circ > 500 ms
- Worst QTcF increase from baseline
 - \circ > 30 ms and < 60 ms
 - o > 60 ms

Two listings will display all the results as presented in "ECG" eCRF page, one on Qualitative Results (rhythm and ECG interpretation) and another one on Quantitative Results (heart rate, PQ/PR duration, RR duration, QRS duration, QT duration, QTcF). All visits and time points will be included in listings.

One additional listing will contain all the information from the "Continuous Holter" eCRF page.

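### SAP 15.7, 16.1.1 and 16.1.2 still tie end-of-treatment PK parameters and QTcF plots to FD 9, although protocol v5.0 moved that profile to FD 10

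*SAP*

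**What the plan says.** **Protocol.** Table 4 (once per FD schedule) puts full PK and ECG profiles on FD 1 and FD 10, and predose and 2.25 h samples on FDs 2, 5, 6 and 7. It has no PK or ECG on FD 9. After the FD 10 dose there are two late points; footnote d says "The 72 and 240-hour timepoints correspond to PTD 1 and 8, respectively", with the earlier one optional. Section 8.3.2 sets the end-of-treatment PK endpoints for FD 9 or FD 10. The Amendment 4.0 rationale (Appendix V) says the profile moved so that the highest end-of-treatment concentration could be monitored.

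**SAP, where it follows the change.** Section 9 separates subjects enrolled before v5.0 (EARLY) from those under it (LATE). SAP Table 4 places the LATE end-of-treatment ECGs on FD 10. The version 2.0 entry in the modification history records new time points for ECG, immune and pharmacodynamic data, but not for PK.

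**SAP, where it does not.**
- 16.1.2 derives parameters "where appropriate for Fraction Day 1, 2 to 6, or 9", then tags each parameter with its days.
- 16.1.2 also says "FD 9 parameters should only be included in descriptive statistics if 4 consecutive days of treatment with no interruption were given to the patient".
- 16.1.1 draws the multiple-dose proportionality plot "using AUC_(0-t), and C_{max} derived from FD9".
- 15.7 runs the overall QTcF plot from -1 to 250 h and gives the second profile panel to FD 9: "Fraction Day 9: Time point (in hours) on the x-axis (From 240 to 250) vs. QTcF observed value on the y-axis".

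**The concern.** The SAP names a profile day on which v5.0 subjects have no PK or ECG samples, and never assigns a PK parameter to the day on which they do. Read literally, it produces no end-of-treatment parameter, accumulation ratio or QTcF profile plot for them. Accumulation is of particular interest in this trial. Protocol 3.1.5 reports a half-life of more than 48 hours against a predicted 8 hours, and accumulation in each subject observed so far. The amendment moved the profile precisely to capture peak exposure.

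**Working it through.** **1. Nominal times.** For FDs 6 to 10, SAP section 9 sets nominal time = (X + 1) × 24 + Y.
- FD 9 predose: 10 × 24 = 240 h; 6 h postdose: 246 h.
- FD 10 predose: 11 × 24 = 264 h; 6 h postdose: 270 h.

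All four agree with SAP Table 4.

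**2. QTcF plots.** LATE dosing-day readings in SAP Table 4: 9 on FD 1, 2 on each of FDs 2, 5, 6 and 7 (8 in total), and 8 on FD 10; 9 + 8 + 8 = 25.
- At or below 250 h: 17. The last is FD 7 at 8 × 24 + 2.25 = 194.25 h.
- Within 240 to 250 h: 0.
- FD 10 readings inside any plot: 0 of 8. By contrast, all 8 EARLY FD 9 readings (240 to 246 h) are inside both ranges.

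The actual-time plots do not help. Ten weekday fractions put FD 10 about 264 h after a Monday start, and 312 h after a start on any other weekday.

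**3. PK days.**

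| | Days |
|---|---|
| Protocol v5.0 samples | FD 1, 2, 5, 6, 7, 10 |
| SAP 16.1.2 parameters | FD 1 to 6, 9 |
| Sampled, no parameter assigned | FD 7, 10 |

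**4. Parameters affected, per v5.0 subject.**
- Tagged FD 9 alone (6): AUC0-tau, CLss/f, Cmin, tmin, and the accumulation ratios for AUC0-6h and Cmax. None can be derived.
- Tagged FD 1 and FD 9 (7): AUC0-6h, AUC0-t, AUC0-t/Dose, Cmax, Cmax/Dose, Cavg, tmax. The end-of-treatment value is not derived.
- Protocol 8.3.2 does not list AUC0-tau or tmin, and lists AUC0-6h for FD 1 only. That leaves 13 - 3 = 10 protocol FD 9/10 endpoints.
- Ctrough (FDs 2 to 6 and 9) covers 3 of 5 v5.0 predose days. C2.25h (FDs 1 to 6 and 9) covers 4 of 6 days.

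**5. How far FD 9 and FD 10 differ.** I assume one compartment, instant absorption, superposition and the weekend gap. The protocol gives a half-life of more than 48 hours (3.1.5) and of approximately 2 days (Amendment 4.0 rationale). At 48 h the 24 h decay factor is r = 2^(-0.5) = 0.7071.
- FD 9: (1 + r + r² + r³) + (r⁶ + r⁷ + r⁸ + r⁹ + r¹⁰) = 2.56 + 0.35 = 2.91 times a first dose.
- FD 10: 1 + 0.7071 × 2.91 = 3.06, which is 5.1% higher.
- At an assumed 96 h: 4.43 then 4.73, which is 6.7% higher.

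**6. AUC0-t cannot simply be switched to FD 10.** The SAP defines it as "The AUC from time zero (= dosing time) to the last quantifiable sampling time", which on FD 10 can be the 240 h sample. At a 48 h half-life:
- Against an FD 9 area ending at 6 h, the FD 10 area to 240 h is 1.051 × (1 - 2^(-5)) / (1 - 2^(-0.125)) = 12.3 times as large.
- Against an FD 9 area to 240 h, which spans the FD 10 dose, it is 21.5% smaller.
- If PTD 8 is counted from the day after the last dose (8 × 24 = 192 h), the figures are 11.9 times and 21.2% smaller.

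**7. Exposure over 0 to 24 h.** AUC0-tau is extrapolated to 24 h, and CLss/f and Cavg are computed from it. On FD 10 the dosing-day samples end at 6 h, and SAP 16.1.2 determines λz on FD 1 only. A day tag alone does not say how the area from 6 to 24 h is obtained. The same gap exists on FD 9.

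**The case against.** The qualifier that opens "where appropriate for Fraction Day 1, 2 to 6, or 9", and the accumulation paragraph of 16.1.2, which gives FD 9 only as an example, could be read as leaving room for FD 10. They do not. The qualifier selects among the listed days, and the definition table restricts both ratios to FD 9 and their inputs to FD 1 and FD 9.

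A stronger point is that much of the FD 10 information is still reported. "Individual PK concentrations in plasma for M3541 will be listed and summarized by dose and fraction day", and 16.1.1 also plots concentration-time profiles by subject and mean profiles by dose and fraction day, so the FD 10 peak is displayed. The FD 7 and FD 10 predose and 2.25 h values appear as concentrations, so the Ctrough and C2.25h gap is largely one of labelling. The ECG listings include every time point, and FD 10 readings enter the worst-QTcF table. PK is descriptive with no formal hypotheses (protocol 8.5.3.2). All of this stands and limits the point to derived parameters and specific plots.

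The table, listing and figure specifications are in a separate document that is not available here, and the sponsor may have used FD 10 there. That is possible, but the SAP is the prespecified text and contradicts its own Table 4.

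Protocol 8.3.2 puts FD 9 and FD 10 in one row, and a 5% difference is small, so pooling could be defended. However, SAP 16.1.1 reports by fraction day: "Pharmacokinetic parameters for M3541 will be listed and summarized by dose and fraction day using standard descriptive statistics".

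**Conclusion.** The point holds and should be fixed. As written, each v5.0 subject has no value for 6 parameters and no end-of-treatment value for 7 more (10 of the 13 being protocol FD 9/10 endpoints), is absent from the multiple-dose proportionality plot, and has 0 of 8 FD 10 dosing-day QTcF readings plotted. The counts rest only on the documents. The FD 9 to FD 10 and AUC0-t comparisons rest on the one-compartment model and the half-life.

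Three stronger readings are not supported:
- A reader might infer that the FD 10 data go unanalysed, or that dose finding is compromised. FD 1 parameters, concentration summaries and plots, ECG listings and the worst-QTcF table remain, and neither the DLT endpoint nor the MTD uses these parameters.
- A reader might infer that the multiple-dose proportionality plot would rest on 8 subjects. Protocol 3.1.5 says only that preliminary data from 8 subjects (3, 4 and 1 at 50, 100 and 200 mg) were available when v5.0 was submitted. It does not give the number enrolled under either version.
- A reader might infer that replacing FD 9 by FD 10 throughout is enough. Steps 6 and 7 show that it is not for AUC0-t, AUC0-tau, CLss/f and Cavg.

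**What to change.** 1. Using the EARLY/LATE split in SAP section 9, define the end-of-treatment profile day as FD 9 (EARLY) or FD 10 (LATE). Apply it to every parameter now tagged FD 9 and to both accumulation ratios. Label the day and report FD 9 and FD 10 as separate fraction days.
2. State how AUC0-tau, and so CLss/f and Cavg, is obtained over 0 to 24 h on the profile day. State that Cmin and tmin use samples within the 24 h interval, which means predose to 6 h.
3. In the multiple-dose proportionality plot, show both profile days, marked, with Cmax and a matched window such as AUC0-6h in place of AUC0-t.
4. Restate the uninterrupted-treatment rule for FD 10 and name the days it covers. The SAP does not say which 4 days it means. If it means every dose since the weekend (FDs 6 to 9), the FD 10 counterpart is FDs 6 to 10.
5. Add FD 7 and FD 10 to Ctrough and C2.25h.
6. Extend the overall QTcF axis past 270 h and add an FD 10 panel from 264 h to past 270 h.

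Cost: SAP wording and modest programming; the samples and ECGs are already scheduled. Separate rows hold fewer subjects, and with one subject SAP section 9 prints the SD as nd. Because FD 10 exposure is expected to be about 5% above FD 9 (up to about 7% at an assumed 96 h half-life), the day must be labelled wherever both appear.

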# 3.1.5 Rationale for Treatment Schedule Changes

At the time of submission of this protocol amendment (Version 5.0 / Amendment 4.0), preliminary data on M3541 safety and plasma concentrations from 8 subjects dosed at 50, 100, or 200 mg once per radiotherapy fraction day (FD; Cohort 1 n=3, 50 mg, cohort 2 n=4, 100 mg and cohort 3 n=1, 200 mg) were available. M3541 was shown to be safe at these dose levels. No DLT or SAEs assessed as related to M3541 were observed. M3541 was detectable in all plasma samples after dosing of the subject, with a rapid early absorption phase. The current PK sampling timepoints, based on a daily M3541 dosing, allowed only for an accurate calculation of  $C_{max}$  but not for PK parameters for a drug with a terminal half-life ( $t_{1/2}$ ) going beyond 24 hours. An extrapolation of the terminal elimination phase derived from postdose plasma concentrations on a non-treatment day and predose after the weekend treatment break suggested a  $t_{1/2}$  of more than 48 hours (versus the anticipated 8 hours based on predictions). Overall, the observed exposure was higher than expected for the 50 mg once per FD dose level and accumulation was observed for each subject. The safety profile was favorable with at most Grade 1 treatment-related toxicities.

Document No. CC

Given these findings, a modification of the dosing schedule is indicated and the proposal takes into account the longer  $t_{1/2}$  and the potential of M3541 accumulation: The ECG and PK sampling schedule is modified accordingly.

The starting dose for the intermittent dose schedules will be based on the available safety and PK data gathered in the first 2 cohorts of the once per FD schedule. As for all dose cohorts, the SMC will finally decide on the dose for each of the 2 intermittent schedules. On an intermittent dosing schedule, the biologically effective dose is expected to be in the range of 100 to 200 mg unless a non-linear exposure increase is observed. However, at the time of submission of the current protocol amendment (Version 5.0 / Amendment 4.0), it is not anticipated that subjects will be dosed according to the intermittent dose schedules as these are unlikely to confer any advantage compared with daily dosing.

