## Major Scientific Changes:

- The DLT follow-up period will now start on the day after the last dose of study treatment rather than 3 days after the last dose of study treatment
- The duration of the DLT follow-up period has been reduced from 3 weeks to 2 weeks. This modification ensures that study subjects who require additional anticancer treatment can receive it as soon as possible following dosing in the study. The 2-week DLT follow-up period reflects 5 times the half-life of M3541 (approximately 2 days) allowing for intersubject variability and is supported by the observation that there is no evidence that M3541 has an active metabolite with a half-life longer than that of M3541. It is therefore considered appropriate to modify the DLT follow-up period based on the half-life of M3541. In addition, based on the available safety data from subjects dosed in the first 2 cohorts, it is not anticipated that modifying the DLT follow-up period in this way will impact the safety data collected in the study. Moreover, to ensure any potential RT-related late toxicities (as may be enhanced by M3541) that occur sometime after the end of the DLT follow-up period are documented, subjects will continue to be followed-up for up to 1 year after treatment, as defined in the previous version of the protocol
- The washout period for prior anticancer therapies is now based on the elimination half-life of the respective therapy, up to a maximum of 15 days, rather than on a fixed 15-day period (exclusion criterion 1)
- Changes to the overall frequency/number of blood samples for PK and pharmacodynamic assessments. Specifically, some PK samples have been removed to reduce the overall volume of blood collected from subjects enrolled in the study. In addition, PK collection at the end of the treatment period will now be on FD 10 so that the highest M3541 plasma concentration experienced by subjects at the end of treatment can be monitored. Pharmacodynamic sampling times are also amended to provide a more comprehensive monitoring of target inhibition throughout the treatment period. Pharmacodynamic and PK sampling times have been matched

whenever possible, except for FD 4/FD 5 and FD 9/FD 10, where pharmacodynamic samples need to be collected 1 day earlier due to the need to process them within 14 hours.

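### CLss/f is labelled steady-state clearance, but at the reported half-life of more than 48 h steady state is not reached by FD 9 or FD 10, so the value is too high

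*SAP*

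**What the plan says.** SAP 16.1.2 lists CLss/f among the individual PK parameters, described as "The apparent total body clearance of drug at steady state following extravascular administration". It equals Dose divided by AUC0-tau, and AUC0-tau is "The AUC from time zero (dosing time) extrapolated to the end of the dosing interval (24 h"). Both are assigned to FD 9 only. The one condition on FD 9 summaries is: "FD 9 parameters should only be included in descriptive statistics if 4 consecutive days of treatment with no interruption were given to the patient".

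Protocol 8.3.2 names CLss/F and Vss/F as secondary PK endpoints on FD 9 or FD 10. Protocol 3.1.5 reports preliminary data that suggested a half-life "of more than 48 hours (versus the anticipated 8 hours based on predictions"), and adds that "accumulation was observed for each subject". The rationale for Amendment 4 (Protocol Appendix V) also works from a half-life of about 2 days. Protocol 6.2.1 and 7.1.2 rule out M3541 on days without radiotherapy, which includes the weekend between FD 5 and FD 6. Protocol v5.0 Table 4 takes the end-of-treatment PK profile on FD 10 and schedules no PK sample on FD 9.

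**The concern.** Dose/AUC0-tau equals clearance only when the amount eliminated over a dosing interval equals the dose. Before that point AUC0-tau is too small and the ratio is too large. With the predicted 8 h half-life, four daily doses would have been ample. With the reported half-life they are not, and the weekend break removes part of the build-up from the first week. The SAP's modification history records an October 2019 version updated after the March 2019 amendment, yet the steady-state formula and the four-day rule remain.

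At stake is a named secondary PK parameter. It would be reported under a label it does not satisfy, with a bias in a known direction that no rule in the SAP detects.

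**Working it through.** The plan gives no figure for the fraction of steady state reached, so there is none to reproduce.

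**Inputs**
- Dosing times follow the nominal-time rule in SAP section 9. FD 1 to FD 5 fall at 0, 24, 48, 72 and 96 h; FD 6 to FD 10 at 168, 192, 216, 240 and 264 h. For FD 9 this is (9 + 1) × 24 = 240 h. The gap from FD 5 to FD 6 is 168 − 96 = 72 h.
- The interval tau is 24 h (SAP 16.1.2).
- The half-life is above 48 h (Protocol 3.1.5). I use 48 h as the lower edge. 36 h and 72 h are my assumptions, to show the range.
- Kinetics are assumed linear and one-compartment, with AUC0-24 measured without error.

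**Formula.** Let k = ln 2 / half-life and r = exp(−24k). A dose given n days before the window adds (Dose/CL) × (rⁿ − rⁿ⁺¹) to the AUC of that window. The steady-state AUC0-tau is Dose/CL. The fraction A of steady state is therefore:
- FD 9 (n = 0 to 3 from FD 9–6, n = 6 to 10 from FD 5–1): A = (1 − r⁴) + (r⁶ − r¹¹)
- FD 10 (n = 0 to 4 and n = 7 to 11): A = (1 − r⁵) + (r⁷ − r¹²)

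CLss/f as defined equals CL/f divided by A, so its overstatement is 1/A − 1.

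**At 48 h** (r = 0.7071)
- FD 9: (1 − 0.2500) + (0.1250 − 0.0221) = 0.853; 1/0.853 − 1 = 17.2%.
- FD 10: (1 − 0.1768) + (0.0884 − 0.0156) = 0.896; 1/0.896 − 1 = 11.6%.

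| Half-life | A on FD 9 | CLss/f too high | A on FD 10 | CLss/f too high |
|---|---|---|---|---|
| 8 h (predicted) | 0.9998 | 0.0% | 1.0000 | 0.0% |
| 36 h (assumed) | 0.899 | 11.3% | 0.936 | 6.8% |
| 48 h (lower edge of reported) | 0.853 | 17.2% | 0.896 | 11.6% |
| 72 h (assumed) | 0.774 | 29.1% | 0.821 | 21.8% |

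**Checks**
- The weekend accounts for much of the bias. Nine consecutive daily doses at 48 h would give 1 − r⁹ = 0.956, an overstatement of only 4.6%.
- The four-day rule, read as FD 6 to FD 9, secures 1 − r⁴ = 75% of steady state at 48 h. The rest of the 85% is carry-over from week 1.
- First-order oral absorption (rate 0.5 to 2 per h) moves the FD 9 figures only to 17.4–17.9% at 48 h and 29.3–29.9% at 72 h.

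**The case against.** The half-life is a preliminary extrapolation from few subjects, and Protocol 3.1.2 reports saturable plasma protein binding in human plasma. If a half-life shorter than the terminal one governs accumulation, the bias is smaller. This stands: the percentages depend on the model, and 72 h appears nowhere in the documents.

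The FD 9 figure also cannot apply to subjects sampled under v5.0, whose full profile is on FD 10. This stands too, and for them the 48 h result is about 12%. It exposes a related gap: SAP Table 4 separates early from late subjects for ECG, pharmacodynamic and immune samples, but SAP 16.1.2 still refers to FD 9 throughout.

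The lambda-z criteria in SAP 16.1.2 (extrapolated area, fit, observation over at least two half-lives) might seem a safeguard. They judge the terminal slope, not whether steady state was reached. Values that fail them are flagged but still summarised.

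A reader might infer that error in carrying AUC from 6 h to 24 h adds to the bias. The documents do not support that, because the SAP names no slope for AUC0-tau and later samples could allow interpolation. Log interpolation from the FD 9 6 h sample to the 72 h sample, which also contains the FD 10 dose, gives 13–15% at 48 h and 26–27% at 72 h, less than the figures above. On FD 10 no dose follows, so under this model log interpolation adds essentially no error.

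A reader might also infer that the bias passes into exposure predictions for the RP2D. No section carries CLss/f there. The model guiding escalation relates DLTs to dose, and the Safety Monitoring Committee reviews available PK data more generally.

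**Conclusion.** The point holds. As written, SAP 16.1.2 labels as steady-state clearance a quantity that, at the protocol's reported half-life and dosing calendar, is not at steady state. Under linear one-compartment kinetics with an accurate AUC0-24, the overstatement at 48 h is about 17% on FD 9 and 12% on FD 10. These are minimum values if the half-life governing accumulation is above 48 h, and they fall if it is shorter. A single range such as 17–29% should not be read as established: its upper end needs an assumed 72 h half-life and an FD 9 profile. The direction of the non-steady-state bias is upward in every case calculated, though negligible at 8 h. The matter concerns labelling and interpretation of a secondary PK parameter and does not touch the primary DLT analysis.

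**What to change.** In SAP 16.1.2:
1. Relabel CLss/f as *apparent Dose/AUC0-24 on that fraction day, not at steady state*, or drop it, and do not interpret it as clearance.
2. Apply the same caveat to the protocol's CLss/F and Vss/F endpoints. SAP section 7 is a natural place to record it. Vss/f is not in the SAP's parameter table, so there is no SAP output to remove.
3. Use FD 9 for subjects enrolled before protocol v5.0 and FD 10 for those enrolled under it.
4. State how AUC is carried from the 6 h sample to 24 h, including which later samples or slope are used.

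These are wording changes and need no new data. If an unbiased CL/F is wanted, a supplementary compartmental fit to each subject's actual dosing history would avoid the steady-state assumption. It is optional and departs from the planned noncompartmental analysis, so it needs its own specification. A noncompartmental lambda-z from the decline after FD 10 is not a dependable substitute. The 72 h sample is optional (Protocol Table 4) and SAP 16.1.2 asks for at least three terminal points, so it may not be estimable in every subject.
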